6.9.1.1. Supporting Analyses of Primary Outcome

An MMRM analysis on the FAS will be performed for the primary parameter.

An ANCOVA model will be used on the last observation carried forward (LOCF) endpoint of HbA1c with fixed effects of metformin use, baseline BMI category, treatment, and baseline HbA1c as a covariate. Within the framework of this ANCOVA model, point estimates and 95% CIs for the mean change from baseline within each treatment group as well as for the difference in mean change from baseline between each investigative treatment group and placebo will be calculated. This analysis will be performed on FAS in addition to the EAS.

Table 6.3 describes the analyses to meet the primary objective, all performed on the HbA1c change from baseline values, including the above sensitivity analyses. The descriptive statistics will also be performed on the HbA1c measurements at each visit.

Table 6.3. Summary of Analyses for Primary Endpoint

Analysis Type	LOCF or Observed Values	Analysis Dataset ^a
MMRM ^b	Observed	EAS
MMRM	Observed	FAS
ANCOVA	LOCF	EAS
ANCOVA	LOCF	FAS

Abbreviations: ANCOVA = analysis of covariance; EAS = efficacy analysis set; FAS = full analysis set; LOCF = last observation carried forward; MMRM = mixed model repeated measures.

^a Refer to Table 6.2.

^b Primary analysis.

6.9.2. Efficacy - Secondary Outcomes

The following secondary efficacy endpoints are going to be analyzed:

- body weight change from baseline to 12 weeks
- percentage of patient with $\geq 5\%$ body weight loss at 12 weeks
- percentage of patients reaching the HbA1c target of $\leq 7.0\%$
- change from baseline of FBG at 12 weeks
- change from baseline of waist circumference at 12 weeks

6.9.2.1. Continuous Variable Analyses

For each continuous endpoint (body weight, FBG, and waist circumference), the observed absolute values and changes from baseline will be summarized using descriptive statistics by scheduled visit. The change from baseline in body weight at 12 weeks, change from baseline in FPG at 12 weeks, and change from baseline in waist circumference at 12 weeks will all be analyzed using a MMRM-based model described in Section 6.1.1.

Body mass index (kg/m^2) will be calculated at each visit at which weight is measured, using height as measured during screening. Change from baseline in BMI will be listed and summarized.

6.9.2.2. Analyses on Variables with Percent of Patients Reaching a Target

The proportion of patients who have $\geq 5\%$ body weight loss at 12 weeks will be analyzed using a logistic regression model with treatment, strata (baseline HbA1c category, and baseline BMI category) and metformin use (yes, no), as fixed effects, and baseline body weight as a covariate. Descriptive statistics will also be presented, including sample size, frequency, and percent.

Additional logistic regression analyses will be performed at 12 weeks for the proportion of patients who have achieved an HbA1c level of $< 7\%$ and HbA1C level of $\leq 6.5\%$. Treatment, baseline BMI category, and metformin use (yes, no) will be fixed effects and continuous baseline HbA1c level will be a covariate. Descriptive statistics will also be presented, including sample size, frequency, and percent.

The proportion of patients who initiated rescue therapy will be summarize by descriptive statistics including sample size, frequency, and percent.

6.9.2.3. Exploratory Analyses

For HbA1C and body weight, a longitudinal dose-response model with titration may be performed. Other exploratory analyses taking account of patients with titration not as planned may also be performed.

6.10. Safety Analyses

Safety analyses will be classified by the actual titration treatment group. Safety descriptive statistic summaries may also include all LY3298176 doses combined, if appropriate. Unless specified otherwise, safety listings will display values/events during all study periods; AEs summaries will be presented for all postbaseline data. For some key summary tables, data will be presented both for the treatment period only and for the treatment period and follow-up period combined, if applicable.

For each patient, treatment period is defined as the date of first treatment dose to last treatment dose date +7 day.

Safety measures will include extent of exposure, vital signs, physical characteristics, TEAEs (including SAEs), adverse events of special interest (AESIs; that is, injection site reactions, hypersensitivity reactions, hypoglycemia episodes, gastrointestinal [GI] events [nausea, vomiting, and diarrhea], acute pancreatitis, and major adverse cardiovascular [CV] events), laboratory measures (including hematology, chemistry, urinalysis, and samples collected for testing for anti-LY3298176 and antibodies), and electrocardiograms (ECGs).

The summary statistics for continuous variables will be sample size, mean, SD, median, minimum, and maximum. If applicable (for example, in the case of MMRM analyses) these descriptive statistics may also include LS means, LS means standard error (SE), and 95% CI for each treatment group, as well as for LY3298176 difference from placebo.

The summary statistics for categorical variables will be sample size, frequency, and percentage.

Additional analyses, such as concentration-safety laboratory plots, may be performed, if warranted, upon review of the data.

6.10.1. Vital Signs

Vital sign measurements (that is, systolic blood pressure [SBP] and diastolic blood pressure [DBP] in mmHg and pulse rate [PR] in beats/minute) will be collected according to the Study Schedule of Events ([Appendix 1](#)). The average 3 measurements for BP and PR will be calculated and analyzed; however, values obtained from fewer than 3 measurements will also be included in summaries and analyses.

Descriptive statistics will be provided by treatment arm for change from baseline at each visit for SBP, DBP, PR. Figures will display LS mean values for change from baseline at each visit for the LY3298176 groups versus placebo.

The above measures will be analyzed using the MMRM-based model described in Section [6.1.1](#). The dependent variable will be the postbaseline change from baseline value for the applicable measure.

The frequency and percentage of patients showing vital sign results in each of the categories specified in [Table 6.4](#) will also be summarized by treatment and visit.

Table 6.4. Vital Sign Summary Categories

Vital Sign Measure	Unit	Low	High
Systolic Blood Pressure	mmHg	≤ 90 and decrease ≥ 20	≥ 160 and increase ≥ 20
Diastolic Blood Pressure	mmHg	≤ 50 and decrease ≥ 10	≥ 100 and increase ≥ 10
Pulse Rate	bpm	< 50 and decrease ≥ 15	> 100 and increase ≥ 15

Abbreviations: bpm = beats per minute.

All vital signs and physical characteristics measurements will be listed.

For pulse rate, a longitudinal dose-response model with titration may be performed, if deemed necessary.

6.10.2. High-Density Lipoprotein Cholesterol, Total Cholesterol, Triglycerides, and Low-Density Lipoprotein Cholesterol

Change from baseline in high-density lipoprotein cholesterol (HDL-C), total cholesterol, triglycerides, and low-density lipoprotein cholesterol (LDL-C) will be analyzed using the ANCOVA model similar to the model used for the supportive analysis on the primary endpoint. The model will include strata (baseline HbA1c category, baseline BMI category, metformin use [yes, no]), treatment, as fixed effects, the applicable baseline measurement as a covariate. The dependent variable will be the postbaseline change from baseline value for the applicable measure.

Descriptive summaries will also be presented.

6.10.3. Adverse Events

No statistical tests will be performed to compare AE rates between treatment groups.

Treatment-emergent AEs, defined as events that are newly reported after randomization or reported to worsen in severity from baseline, will be determined based on occurrence, on or after the date of first dose of investigational product.

Adverse events will be summarized as TEAEs. Summaries of TEAEs will be presented for the combined treatment and follow-up periods. A few selected tables may be presented for both the treatment period only, and the combined treatment and follow-up period.

Adverse event summary tables will include a “Total LY3298176” column for all LY3298176 treatment groups combined, if appropriate.

In summaries by System Organ Class (SOC) or Preferred Term (PT), SOC will be displayed in alphabetical order and PT will be displayed by decreasing frequency of the “Total LY3298176” patient incidence within each SOC. In summaries by PT, PT will be displayed by decreasing frequency of the “Total LY3298176” patient incidence. Ordering by frequency should be based on percentages and not on frequency counts.

All AEs (not only TEAEs) will be presented in listings by patient, actual term, PT, severity, and relationship to treatment (yes, no). Listings will also include treatment group, start date, and stop date (or ongoing), assessment of seriousness, relationship to nonstudy drug treatment (study disease, study procedure, none), relationship to study device (yes, no), action taken with study medication, and outcome of AE.

Listings will report data as recorded (for example, unknown severity or relationship and partial or unknown dates). Where necessary, such as for determination of TEAEs, partial or unknown dates will be imputed.

6.10.3.1. All Treatment-Emergent Adverse Events

The incidence of patients with at least 1 TEAE and the patient incidence of TEAEs will be summarized, showing frequency and percentage of patients, by SOC, PT, and treatment group. The total number of TEAEs and the number of TEAEs for each SOC and PT will also be reported for each treatment group.

The patient incidence of TEAEs will also be summarized by SOC, PT, maximum severity, and treatment group.

6.10.3.2. Related Adverse Events

The incidence of patients with at least 1 TEAE assessed as related (including possibly related or unknown) and the patient incidence of related TEAEs will be summarized by SOC, PT, and treatment group. In addition, the total number of related TEAEs and the number of related TEAEs for each SOC and PT will be reported for each treatment group.

6.10.3.3. Serious Adverse Events

A listing of all SAEs by patient will be produced. If a sufficient number of SAEs are reported (that is, >1 SAE overall per treatment group or >3 SAEs in any 1 treatment group) summary tables will be produced showing the incidence of patients with at least 1 SAE and the patient incidence of SAEs by SOC, PT, and treatment group. In addition, if a sufficient number of SAEs

are reported, the total number of SAEs and the number of SAEs for each SOC and PT will be reported for each treatment group.

6.10.3.4. Adverse Events Leading to Discontinuation

Treatment-emergent AEs reported with an action taken of “drug withdrawn” will be summarized, using patient incidence, by SOC, PT, and treatment group. In addition, a listing of AEs leading to discontinuation of study treatment (that is, with action taken as “drug withdrawn”) will be presented.

Treatment-emergent AEs reported as reason for study discontinuation (that is, discontinuation of study procedures as well as study treatment) will be summarized, using patient incidence, by SOC, PT, and treatment group. In addition, a listing of AEs leading to discontinuation of study will be presented.

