9.2.1.2.1. Nausea, Vomiting, and Diarrhea

Nausea, vomiting, and diarrhea events will be recorded on a specific eCRF. They should not be recorded as AEs unless the event meets an SAE criterion. For each event, assessment of severity, duration, and investigator's opinion of relatedness to study drug and protocol procedure will be captured.

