10.3.4.2. Adverse Events

Adverse events will be listed by patient, actual term, preferred term, severity, and relationship to the treatment. Adverse events will be summarized as TEAEs (defined as events that are newly reported after randomization or reported to worsen in severity from baseline). The incidence of patients with at least 1 TEAE and the incidence of TEAEs by preferred term and system organ class will be presented by treatment group. The frequency and percentage of TEAEs will be presented. The incidence of patients with at least 1 TEAE assessed as possibly related to the investigational drug will be summarized by treatment group, in addition to the incidence of these possibly related TEAEs by preferred term. In addition, a summary of TEAEs by severity will be presented descriptively by treatment group.

Reported thyroid and adjudicated CV and pancreatic-related AEs will be listed by patient, and if there are a sufficient number of cases, they may be summarized by treatment group.

All SAEs will be listed by patient. If a sufficient number of SAEs are reported, incidence summaries similar to incidence of TEAEs will be included.

Discontinuations due to TEAEs will be listed by patient and summarized by treatment group.

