4.2. Secondary Objectives

The secondary objectives are to compare each titration scheme to placebo at 3 months for the following secondary efficacy parameters:

- proportion of patients achieving HbA1c target of <7.0%
- the change in fasting blood glucose (FBG) (central laboratory) from baseline
- the change in body weight from baseline
- the change in waist circumference from baseline
- incidence of treatment-emergent adverse events (TEAEs) and serious adverse events (SAEs)
- incidence of nausea, vomiting, and diarrhea
- discontinuation of study drug due to adverse events (AEs)
- incidence and rate of hypoglycemia (severe, total, documented symptomatic, and nocturnal)
- incidence of anti-LY3298176 antibodies

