6.10.4. Adverse Events of Special Interest

Adverse events of special interest to be identified and described during this study are injection site reactions, hypersensitivity reactions, hypoglycemia, acute pancreatitis, major adverse CV events, and selected GI events (nausea, vomiting, and diarrhea).

Descriptive statistics for AESIs will be presented by treatment group and visit. Continuous responses will be summarized using sample size, mean, SD, median, minimum and maximum, while categorical responses will be summarized using sample size, frequency, and percentage.

In addition, for AESIs with information collected on the AE eCRF page (that is, hypersensitivity reactions, acute pancreatitis, and major adverse CV events) summary tables will be presented only if $>3\%$ of patients have the AESI. The incidence of patients with at least 1 AESI and the

patient incidence of AESIs will be summarized, showing frequency and percentage of patients, by SOC (if applicable), PT, and treatment group. The total number of AESIs and the number of AESIs for each SOC (if applicable) and PT will also be reported for each treatment group.

Listings by patient will be provided for AESIs. Listings will also present adjudication information by patient for adjudicated events.

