6.10.4.3. Nausea, Vomiting, and Diarrhea

Nausea, vomiting, and diarrhea event information will be collected on a designated separate eCRF page. Summaries and analyses for incidence will be provided for each randomized treatment group and by visit.

The prevalence and incidence of nausea, vomiting, and diarrhea will be summarized by the treatment and the time interval of interest. In addition, similar tables will also be generated by actual dose and time interval. The duration of each event will also be computed in days as event stop date minus event start date. For computation purposes, events that are ongoing will be considered censored (that is, ended) at the date of last study contact.

The maximum severity and duration from baseline to Week 12 of nausea, vomiting, and diarrhea will be summarized by treatments.

Plots with the percentage number of subjects with the events versus initiation time course will also be generated. The y-axis is the percentage of subjects with the specified AE and the x-axis is the time since the first dose.

A listing with GI TEAEs of interest will be provided.

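### The table of drug stops due to AEs draws only on AE records marked 'drug withdrawn', and non-serious nausea, vomiting and diarrhea are kept off those records

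*SAP*

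**What the plan says.** **Endpoint.** Protocol Table GPGF.2 and SAP 4.2 both list drug discontinuation due to AEs among the secondary endpoints. Protocol 10.3.4.2 adds: "Discontinuations due to TEAEs will be listed by patient and summarized by treatment group".

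**Counting rule.** SAP 6.10.3.4 summarizes, by treatment group, "Treatment-emergent AEs reported with an action taken of" 'drug withdrawn', and lists the same events. It names no other source for drug stops. Action taken appears in the SAP as an item of the AE listings in 6.10.3 ("action taken with study medication, and outcome of AE") and again in 6.10.3.4.

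**Recording rule.** Protocol 9.2.1.2.1 places nausea, vomiting and diarrhea on a specific form and says: "They should not be recorded as AEs unless the event meets an SAE criterion". The items it names are severity, duration and causality ("opinion of relatedness to study drug and protocol procedure will be captured"). SAP 6.10.4.3 agrees on the location: "Nausea, vomiting, and diarrhea event information will be collected on a designated separate eCRF page". SAP 6.10.4 names three special-interest events as held on the AE page: hypersensitivity, acute pancreatitis and major cardiovascular events. The GI events are not among them.

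**Parallel rules.** Protocol 9.2.1.2.4 keeps non-serious hypoglycemia off the AE record in the same way. Protocol 9.2.1.2.2 is slightly softer for injection site reactions, which need not be recorded as AEs unless serious. SAP 6.10.4.2 says those meeting SAE criteria will also be collected as AEs.

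**The concern.** Followed literally, the two rules do not meet. A patient who stops drug for persistent but non-serious vomiting has the event on the GI form, has no AE record, and so has no AE with action taken 'drug withdrawn'. The table for the secondary endpoint would not count that patient.

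This would be minor in many trials. Here, Protocol 5.1 says the data are to support the titration scheme with the fewest GI events for Phase 3, and Protocol 5.5 describes 15 mg in Phase 1 as safe but not well tolerated. A drug stop for non-serious nausea, vomiting or diarrhea is therefore the kind of stop most informative for choosing among the three schemes. If it is missing, each active arm can look better tolerated than it was, and the schemes cannot be fairly compared on this endpoint.

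**Working it through.** The plan gives no figure to reproduce. The check is a trace from form to table, followed by one scaling calculation.

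**Step 1: what reaches the table.** Three things are needed: an event treated as a TEAE, an action-taken value attached to it, and that value being 'drug withdrawn' (SAP 6.10.3.4).

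| Event | Where recorded | Action taken named? | Reaches the 6.10.3.4 table? |
|---|---|---|---|
| Serious nausea, vomiting or diarrhea | AE record as well (Protocol 9.2.1.2.1) | Yes, as an AE record | Yes |
| Other GI symptoms | AE record | Yes | Yes |
| Non-serious nausea, vomiting or diarrhea | GI form only | No | Only if pooled with an action taken |
| Non-serious hypoglycemia | Hypoglycemia form only | No | Only if pooled with an action taken |
| Non-serious injection site reaction | Injection site form; AE record not required | No | Only if also entered as an AE, or pooled with an action taken |

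**Step 2: is pooling stated?** No sentence in either document says the special-form records enter the TEAE data, or gives them an action taken. The SAP does spell out several source pages where it wants them: SAP 6.10.3.6 counts deaths from the status, AE or SAE pages. SAP 6.10.3.4 has no such sentence. Its second part, on TEAEs leading to study discontinuation, has the same gap.

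**Step 3: do other routes fill the table?**
- SAP 6.2 summarizes the primary reason for stopping treatment, but 6.10.3.4 does not use it, so the two tables can show different counts.
- Protocol 9.2 requires a stop caused by an AE to be reported by eCRF, without naming the page.
- Protocol 8.1.1 and 9.2.1.2 require an immediate alert for any event that the investigator thinks warrants permanent discontinuation. That is a notification, not a table source.

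**Step 4: scale.** Planned arm size is 92/4 = 23 (Protocol Synopsis). Each omitted patient lowers that arm's percentage by 1/23 = 4.3 points; k omitted patients lower it by k/23. For illustration, k = 0, 1, 2 gives 0, 4.3 and 8.7 points. The documents give no rate of AE stops or GI stops, so k cannot be derived.

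**The case against.** The strongest reply is that everything turns on a form that is not in the documents. Protocol 9.2.1.2.1 says what the GI form captures; it does not say that nothing else is captured. Several places also speak of these events as AEs. Protocol 10.3.4.1 counts AESIs within TEAEs. SAP 6.10.4.3 promises a listing of GI TEAEs and plots the share of subjects with the AE in question. SAP Table 6.8 includes an injection-site term among TEAEs. SAP 6.10.3 defines TEAEs by occurrence and timing, not by page.

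This stands in part: pooling may well be intended, and the effect is then zero. But treating the events as TEAEs is not enough, because the filter still needs an action-taken value that no text gives these forms.

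It is also fair that the cause of a stop should be somewhere in the data (Protocol 8.1.2, 9.2; SAP 6.2), that GI incidence, severity and duration are reported regardless (SAP 6.10.4.3), and that no tests are planned on AE rates (SAP 6.10.3). The table is descriptive and the primary analysis is untouched.

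Three stronger readings are tempting, and the documents do not support them.
- *SAP 6.10 lists AESIs beside TEAEs, so the GI events must lie outside TEAEs.* That same list includes hypersensitivity, pancreatitis and major cardiovascular events, which SAP 6.10.4 puts on the AE page. Being listed beside TEAEs shows nothing.
- *No planned table will show how many stops were due to GI events.* That holds only if the forms are not pooled; if they are, 6.10.3.4 reports by preferred term.
- *The shortfall could be gauged from planned attrition: (92 − 80)/4 = 3 per arm, 3/23 = 13.0%.* The 13% in Protocol 10.1 is an all-cause dropout allowance. It says nothing about AE stops, and patients who stop drug are asked to stay in the study.

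**Conclusion.** The conflict between the recording rule and the counting rule is real and should be resolved. As written, SAP 6.10.3.4 omits drug stops due to non-serious nausea, vomiting or diarrhea, and can omit those due to non-serious hypoglycemia or injection site reactions, unless the special forms are pooled into TEAEs with an action taken. Some wording hints at pooling; nothing states it.

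The size is 4.3 points per omitted patient in an arm of 23. The number of such patients is unknown and may be zero. Confidence is medium because the eCRF cannot be inspected. A reader should not infer that the table will miss all GI-related stops: serious events and other GI symptoms reach it in any case.

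**What to change.** In SAP 6.10.3.4, count a patient as discontinuing study drug due to an AE if either condition holds:

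1. a TEAE has action taken 'drug withdrawn'; or
2. the primary reason for stopping treatment in SAP 6.2 is an adverse event, including an event held on the nausea/vomiting/diarrhea, injection site or hypoglycemia form.

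Within that count, show the number due to nausea, vomiting or diarrhea in each arm. Using both sources matters, because a single primary reason can hide a GI stop behind missed doses or patient decision. If pooling with an action taken is already built into the data, say so in the same section.

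The cost is one extra derivation before lock, and matching by date to the special form where the disposition page does not name the event. Reported AE-discontinuation rates may rise in the active arms. Some stops could still be missed: Protocol 8.1.2 requires a permanent stop after 2 or more missed doses for any reason, and no text says which reason is entered when the doses were withheld for vomiting. That is a separate matter of site conduct, which this derivation does not settle.
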